8.3 Treatment with Crenolanib (CP-868,596)

This study involves an assessment of crenolanib administered orally for the treatment of relapsed /refractory AML with FLT3 activating mutations. Responding patients who proceed to allogeneic stem cell transplant may be candidates to continue crenolanib as maintenance post-transplant.

All patients receiving study drug in relapse or with refractory disease will be administered 200mg/m²/day divided as three times a day (preferably every eight hours) daily, taken orally at least 30 minutes pre or post meal. Patients will complete a daily diary to record the date, time, and amount (number of tablets) of crenolanib taken and if it was taken either with or without food. (Appendix III). Tablets should be swallowed whole and not be crushed or dissolved.

Dosing will be three times daily, beginning on Day 1 through Day 28, for a 28 day cycle. The starting dose will be 200mg/m²/day divided as three times a day (preferably every eight hours) (Table 8.1). The start of a cycle is denoted by the ingestion of study drug.

Table 8.1. Baseline Treatment Regimen

Regimen	Dose					
All patients	Day 1 through Day 28					
	200mg/m ² /day divided as three times a day					
	(preferably every eight hours)taken orally at					
	least 30 minutes pre or post meal					

Patients may receive multiple cycles of treatment as described in Section 8.7.5.

The investigator or his/her designee is responsible for explaining the correct use of the investigational agent(s) to the patient/site personnel, verifying that instructions are followed properly, maintaining accurate records of study drug dispensing and collection, and returning all unused medication to AROG or its designee at the end of the study. Study medication that has been dispensed but remains unused at the end of the cycle is recorded by the site personnel and either safely discarded, if opened, or returned, if unopened.

Patients will be instructed to contact the investigator as soon as possible if they have a complaint or problem with the study drug so that the situation can be handled. If a patient vomits after drug ingestion, no replacement dose is to be taken; the patient can continue to take the remaining doses as planned. Missed doses will not be made up, and leftover drug should be returned to the study site upon patient follow up.

Counting Cycle Days: If drug is held or a dose is missed, the missed/held dose should not be made up. Dosing will resume with the next scheduled dose. The patient should enter in the diary the doses as missed. If drug is held or missed for a day or more, the cycle should continue as if uninterrupted. Counting days of a cycle should be ongoing without disruption. The start of cycle 1 is denoted by the ingestion of study drug. The scheduled procedures/visits should comply with the study calendar regardless of amount of study drug administered in a 28 day cycle.

Continuation of crenolanib after allogeneic transplantation as maintenance therapy:

Crenolanib will be held during the transplant period by stopping drug 72 hours prior to start of conditioning and resuming no sooner than 30 days post stem cell infusion.

For patients in CR/CRi after allogeneic transplant, crenolanib may be resumed at the same dose of crenolanib tolerated as induction when crenolanib was held. Patients will complete a daily diary to record the date, time and amount (number of tablets) of crenolanib taken and if it was taken either with or without food (Appendix III). Tablets should be swallowed whole and not be crushed or dissolved/

Patients may receive multiple cycles of treatment as described in Section 8.7.5. Follow up of patients on post-transplant crenolanib is outlined in section 8.2

The investigator or his/her designee is responsible for explaining the correct use of the investigational agent(s) to the patient/site personnel, verifying that instructions are followed properly, maintaining accurate records of study drug dispensing and collection, and returning all unused medication to AROG or its designee at the end of the study. Study medication that has been dispensed but remains unused at the end of the cycle is recorded by the site personnel and either safely discarded, if opened, or returned, if unopened.

Patients will be instructed to contact the investigator as soon as possible if they have a complaint or problem with the study drug so that the situation can be handled. If a patient vomits after drug ingestion, no additional tablets should be taken on that day. Missed doses will not be made up, and leftover drug should be returned to the study site upon patient follow up

Counting Cycle Days: If drug is held or a dose is missed, the missed/held dose should not be made up. Dosing will resume with the next scheduled dose. The patient should enter in the diary the doses as missed. If drug is held or missed for a day or more, the cycle should continue as if uninterrupted. Counting days of a cycle should be ongoing without disruption. The start of cycle 1 is denoted by the ingestion of study drug. The scheduled procedures/visits should comply with the study calendar regardless of amount of study drug administered in a 28 day cycle.

8.4 Materials and Supplies

Crenolanib besylate is supplied as 100mg and/or 20mg tablets for oral administration in 42 count bottles or 30-count bottles. Crenolanib besylate tablets should be refrigerated at a temperature between 2°C and 8°C (35.6°F and 46.4°F). Standard household refrigeration is considered adequate for drug storage. Crenolanib should be stored in the vials provided by the pharmacy and kept out of the reach of children. Used bottles and unused tablets and bottles should be returned to the treating physician before starting a new therapeutic cycle to assess treatment compliance. Study drug will be supplied by AROG Pharmaceuticals, LLC. Study drug may be packaged by a third party. Clinical trial materials will be labeled according to regulatory requirements.

8.5 Method of Assignment to Treatment

All patients will receive crenolanib. Patients who meet all criteria for enrollment will be considered enrolled into the study at Day 1 of Cycle 1.

8.6 Rationale for Selection of the Baseline Dose for Current Protocol Version 4 Dose of 200mg/m²/day divided as three times a day

In vitro experiments have demonstrated that crenolanib inhibits the phosphorylation of FLT3-D835 (FLT3-D835Y/H) and FLT3-ITD mutations with an IC50 of approximately 9nM and 2nM, respectively, in culture medium. In studies performed on plasma, the IC50 observed was 34nM against the FLT3-ITD mutation (23). FLT3 inhibition studies suggest that sustained inhibition of FLT3 phosphorylation approximately 10-15 fold above IC50 is required to achieve meaningful clinical benefit, taking into account FLT3 expression in both stromal and blast cells. We hypothesize that at least 680nM, or 20-fold the IC50, is needed for crenolanib to penetrate into bone marrow and maintain a sustained minimum concentration.

Crenolanib serum concentration-time data were modeled with a two-compartment structural model using a maximum likelihood estimation method as implemented in ADAPTII. Individual Bayesian post hoc parameter estimates were obtained for the volume of distribution of the central compartment (V_c), elimination rate constant (K_c), and the intercompartmental transfer rate constants (K_{cp} and K_{pc}). These parameter values were then extrapolated to a new population of 1,000 patients by pooling and random resampling. The concentration-time curves were then simulated out to steady-state (100 mg TID) using a differential equation solver for a two compartment model with first-order absorption and first-order elimination scripted in R. This Monte Carlo resampling scheme accounts for the variability in pharmacokinetic parameters and

allows for estimation of 95% confidence intervals of the concentration-time estimates indicated by the shaded regions on the plots below (figure 8.1).

The modeling/simulation cycle described above was performed with combined data from two adult studies (19 patients, ARO-BRE-001 (NCT01229644) and 002 (NCT01243346)) and one pediatric study ARO-003 (NCT01393912). This data was used to perform distribution of the BSA-normalized crenolanib pharmacokinetic parameters and the expected distribution of BSA in an adult population to perform 1,000 Monte Carlo simulations for each regimen. In figure 8.1, the shaded regions represent the 95% CIs for each simulation. The patients' dosing interval is considered to be every eight hours. Although the drug would be administered three times a day on a "TID" schedule, it is important to understand that the simulation was performed using an every eight hour dosing schedule and every attempt should be made to dose the drug on this schedule.

[figure not shown]

Figure 8.1. The PK simulation for TID (median +/- SD) plotted based on a simulation of data from 19 adult patients and pediatric patients.

The serum PK results of the 16 AML patients enrolled to date at 100mg TID across two clinical studies show that fifteen have cycle 1 day 15 average trough levels of 444nM (standard error ±15nM), below the theoretical target of 680nM required to inhibit FLT3 signaling in bone marrow. In addition, the Pk data suggest that crenolanib is slowly absorbed with a t-max of 2-4 hours and mean terminal half-life ranging from 8.6-9.5 hours. This suggests the currently administered crenolanib dose of 100mg TID (protocol v3) is insufficient to achieve adequate sustained inhibition of FLT3 kinase activity. As of May 2013, of the 16 patients enrolled across two clinical studies, 4 have achieved a CR (1CR/3CRi) with 6 others having some short lived reduction in blast cells in either blood or marrow and another 4 patients showing no response. In the 6 patients with blast decrease, blast reduction occurred by 21 days but was not sustained. These results suggest pharmacologic failure for most patients at this initially selected dose of 300mg/day (100mg/TID). In addition, AML patients over 85kg did not achieve sustained responses and are potentially underdosed on a flat-dose schedule.

In contrast to the flat mg/day dosing schedule currently given on this trial under protocol v3, an ongoing phase I trial (NCT01393912) in pediatric patients with malignant brainstem glioma has treated 49 patients at four escalating dose levels of single agent using mg/m2/day dosing. Nine patients have received crenolanib at 220mg/m2 QD as a single daily dose. Six out of these 9 patients were on study drug for the DLT period of 28 days. Two patients experienced DLT of transaminase elevations and stopped crenolanib therapy with subsequent resolution of abnormal

labs. Thus in the pediatric population 220mg/m2 given as one single daily dose approaches MTD but otherwise yields no other significant toxicities.

Because a single daily dose achieves higher peak concentrations of drug, we have hypothesized that once daily dosing is associated more commonly with potential toxicities such as LFT elevations; and a BID or TID schedule will lower peak drug concentrations potentially allowing more sustained dosing, less toxicity and improved pharmacokinetic profiles. At the current 100mg TID dose prescribed in this trial (protocol version 31) no substantial drug related toxicities have been observed. The most common drug related adverse events (AEs) reported as grade 1 or 2 nausea and vomiting. Two patients required dose reductions for Grade 3 and 4 transaminitis, which resolved once drug was held. Both were on two CYP3A4 inhibitors which may interfere with drug metabolism. Both patients tolerated 80 mg TID without transaminitis. A crenolanib dose of 200mg/m²/day given as a TID schedule is postulated to result in a lower peak drug concentration and potential toxicities but provide adequate sustained dosing levels to reduce pharmacologic failure. Pharmacokinetic data will continue to be collected.

8.7 Dosing and Dose Modification of Crenolanib

Protocol: ARO-004

Toxicities will be graded using the NCI CTCAE, Version 4.03 (see partial representation in Appendix VI).

All patients with relapsed/refractory AML will receive crenolanib induction therapy at a starting oral dose of 200mg/m²/day divided three times a day (preferably every eight hours) continuously for 28 days for each cycle of treatment. Study drug should be taken at least 30 minutes prior to or following a meal..

Crenolanib will be held starting 72 hours prior to start of planned conditioning for HSCT. Study drug will be held for a minimum of 30 days post infusion of stem cells (day of HSCT).

Post HSCT crenolanib will resume at the dose level last tolerated prior to HSCT.

BSA will be capped at $2m^2$ for large patients and $1.5m^2$ for small patients. Therefore the highest starting study drug dose will be 400 mg/day ($2m^2 \times 200 \text{mg/m}^2/\text{day}$) and lowest drug dose will be 240 mg/day ($1.5m^2 \times 160 \text{mg/m}^2/\text{day}$ -see dose reduction scheme table 8.4).

Because dosing increments based on BSA may not result in uniform doses given TID, the sponsor will provide detailed dosing instructions to the site. Upon enrollment, the site will provide the sponsor the patient's height, weight and BSA. Along with the acknowledgement of enrollment, the sponsor will provide the site with a dosing information sheet (Appendix XV) on which will be the calculated starting dose (dose level 0) with instructions for how much drug should be taken at each TID ingestion. Similar instructions will be provided on the dosing instruction sheet for dose level (+1), (-1) and (-2) should the patient require dose modification while participating on the study.

Patients currently enrolled under protocol version 3 can be continued at their current dose and dose escalated as defined in this protocol version 4 if without grade 3 or 4 toxicity and lack of response to study drug at the current dose.

Patients are strongly encouraged to be premedicated as for moderate to highly emetogenic therapy per ASCO 2011 guidelines. Patients will complete a daily diary to record the date, time and amount (number of tablets) of crenolanib taken, and if it was taken with or without food. (Appendix III)

Dose Escalation during induction and maintenance

There will be one level dose escalation allowed for patients who do not experience grade 3 or 4 toxicity and who have no response based on investigator evaluation.

Table 8.2: Dose escalation guidance

Dose level	Crenolanib dosing
0	$200 \text{ mg/m}^2/\text{day}$
+1	$220 \text{ mg/m}^2/\text{day}$

Dose escalation can occur as early as cycle 1 day 15.

Protocol: ARO-004

Counting Cycle Days: If drug is held or a dose is missed, the missed/held dose should not be made up. Dosing will resume with the next scheduled dose. The patient should enter in the diary the doses as missed. If drug is held or missed for a day or more, the cycle should continue as if uninterrupted. Counting days of a cycle should be ongoing without disruption. The start of cycle 1 is denoted by the ingestion of study drug. The scheduled procedures/visits should comply with the study calendar regardless of amount of study drug administered in a 28 day cycle.

8.7.1 Dose Reductions for Crenolanib for Non-hematologic Toxicities During Reinduction and Post Allogeneic Transplant

Toxicities will be graded using the NCI CTCAE, Version 4.03 (Appendix VI).

For patients receiving crenolanib for reinduction therapy: Dose reductions for non-hematologic toxicities except nausea, vomiting, and diarrhea due to crenolanib will be done according to the schema in Table 8.3. Dose reductions are summarized in Table 8.4 and reductions below 160mg/m²/day will lead to withdrawal from the study drug, in which case the patient will stop taking crenolanib, but will still be followed for outcomes as outlined in 8.12.

Table 8.3. Based on NCI CTCAE v4.03, Crenolanib Dose Reduction for Non Hematologic Toxicities Except Nausea, Vomiting, and Diarrhea related to study drug. Use toxicity grade at time of start of next planned cycle. Reassessment may be performed weekly to determine when to restart drug or dose modify. A 28-day deferment window is allowed to assess toxicities.

Toxicity (NCI Criteria)	Dose modification for patients taking crenolanib as reinduction
Grade 1 or 2	No dose modification
Clinically significant or persistent grade 2 despite optimal therapy	Hold drug until toxicity resolves to grade 1 or less. Restart drug at same dose level (Table 8.4).
Grade 3 or 4	Hold drug until toxicity resolves to grade 1 or less. Restart drug at next-lower_dose level (Table 8.4).

Table 8.4. Dose levels of Crenolanib During Reinduction

Dose Level	Crenolanib Daily Dose
Baseline	200mg/m ² /day
First dose reduction (-1)	180 mg/m ² /day
Second dose reduction (-2)	160 mg/m ² /day

For patients receiving maintenance crenolanib after allogeneic transplant: Start of maintenance crenolanib therapy is intended at the earliest time no sooner than 30 days but no longer than 90 days after allogeneic HSCT. Prerequisites for start of maintenance are a stable dose of immunosuppressive drugs for management or prophylaxis of GVHD or no escalation of therapy for GVHD within 14 days of starting study drug and/or have no more than Grade 2 persistent non hematological toxicity related to the transplant. Patients must have received crenolanib prior to HSCT to continue on to maintenance.

Maintenance therapy will start at the last dose tolerated during reinduction therapy. For example, if the patient was taking 180mg/m2/day prior to proceeding with HSCT, maintenance therapy will resume at 180mg/m2/day.

Dose reductions for non-hematologic toxicities except nausea, vomiting or diarrhea due to crenolanib will be done according to the schema in Table 8.5. For dose level reductions please refer to Table 8.6, and appendix XV. Dose reductions below 140 mg/m2/day are not planned and crenolanib will be stopped.

Table 8.5. Based on NCI CTCAE v4.03, Crenolanib Dose Reduction for Non-Hematologic Toxicities Post Allogeneic Transplant except Nausea, Vomiting, or Diarrhea related to study drug. Use toxicity grade at time of start of next planned cycle. Reassessment may be

performed weekly to determine when to restart drug or dose modify. A 28-day deferment window is allowed to assess toxicities.

Toxicity (NCI Criteria)	Dose modification for patients taking crenolanib post allogeneic transplant
Grade 1 or 2	No dose modification
Clinically significant or persistent grade 2 despite optimal therapy	Hold drug until toxicity resolves to baseline or grade 1 or less. Restart drug at same dose level (Table 8.6).
Grade 3 or 4	Hold drug until toxicity resolves to baseline or grade 1 or less. Restart drug at next lower dose level (Table 8.6).

Table 8.6. Dose adjustments of Crenolanib Post Allogeneic Transplant Maintenance therapy will start at the last dose level tolerated during reinduction therapy and dose adjustments made from that dose.

Current crenolanib dose:	Change crenolanib dose to:
100 mg PO TID*	80 mg PO TID
220 mg/m2/day	200 mg/m2/day
200 mg/m2/day	180 mg/m2/day
180 mg/m2/day	160 mg/m2/day
160 mg/m2/day	140 mg/m2/day

^{*}for patients enrolled on v3 of this protocol, not on BSA-based dosing

8.7.2 Dose Reductions for Crenolanib for Hematologic Toxicities for Patients Taking Crenolanib as Reinduction and Post Allogeneic Transplant

Patients with leukemia usually present with abnormal peripheral blood counts at the time therapy is started and myelosuppression is an expected event during the course of therapy for acute leukemia. Thus, no dose adjustments or treatment interruptions for myelosuppression will be planned for the first two cycles of therapy. After this time, treatment interruptions and dose adjustments may be considered according to the following guidelines:

Patients with neutropenia or thrombocytopenia as a consequence of the disease do not require treatment interruptions for myelosuppression. Dose-reductions in these patients should be considered in an individual case and discussed with the medical monitor. The following guidelines can be used for these patients:

- Patients with pre-cycle counts of neutrophils >1x10⁹/L and platelets >100 x10⁹/L and no evidence of residual leukemia who have sustained neutropenia <0.5 x10⁹/L or platelet counts <25 x x10⁹/L for more than 4 consecutive weeks in the current cycle, may receive a subsequent cycle at 1 dose level reduction. A reduction of 2 dose levels may be considered if the myelosuppression was deemed severe and life threatening by the treating physician, and if it is in the patient's best interest.
- If there are persistent peripheral blood blasts, or the bone marrow shows >5% blasts, treatment may continue regardless of neutrophil and platelet count with supportive care as needed.
- Patients with pre-cycle counts of neutrophils $<1x10^9/L$ and platelets $<100 x10^9/L$ and no evidence of residual leukemia, consider holding therapy until recovery of granulocytes to $\ge 1 x10^9/L$ and platelets $\ge 60 x10^9/L$, then resume at same or 1 lower dose level according to guidelines mentioned above.

For patients taking crenolanib post allogeneic transplant, dose modification for hematologic toxicity will follow those outlined in Section 8.7.1 and tables 8.5 and 8.6

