8.12 Follow up Visits

The Study Schedule in Appendix IV lists the specific follow up visits for this study.

The Study Schedule applies to patients receiving study drug. The calendar should re-commence as start of cycle 1 when drug is resumed post allogeneic transplant. Patients who have discontinued study drug for any reason should be followed for survival.

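### Section 8.7.2 leaves two unreconciled instructions for low blood counts during post-transplant maintenance, one of them pointing to a table captioned for non-hematologic toxicity

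*Combined protocol and SAP*

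**What the plan says.** The heading of Section 8.7.2 takes in both phases of treatment: "Dose Reductions for Crenolanib for Hematologic Toxicities for Patients Taking Crenolanib as Reinduction and Post Allogeneic Transplant". Its first paragraph gives a reason, "Patients with leukemia usually present with abnormal peripheral blood counts at the time therapy is started", and then the rule: "no dose adjustments or treatment interruptions for myelosuppression will be planned for the first two cycles of therapy". After those cycles, interruptions and adjustments may be considered under the guidelines that follow. The section ends with a sentence on maintenance: "For patients taking crenolanib post allogeneic transplant, dose modification for hematologic toxicity will follow those outlined in Section 8.7.1 and tables 8.5 and 8.6".

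The place it points to is written for something else. The title of Section 8.7.1 names non-hematologic toxicities, and so does the caption of Table 8.5: "Crenolanib Dose Reduction for Non-Hematologic Toxicities Post Allogeneic Transplant except Nausea, Vomiting, or Diarrhea related to study drug". For grade 3 or 4 that table holds drug until recovery to baseline or at most grade 1, then restarts one level lower on Table 8.6. For clinically significant or persistent grade 2 it holds and restarts at the same level. Its caption says to use the grade present when the next planned cycle starts.

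Two other sections bear on the point. Section 8.12 says: "The calendar should re-commence as start of cycle 1 when drug is resumed post allogeneic transplant". Section 8.3 allows maintenance to begin with incomplete count recovery: "For patients in CR/CRi after allogeneic transplant, crenolanib may be resumed".

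**The concern.** Read in order, the section gives a rule that appears to cover all patients and then a second rule for some of them, without saying how the two fit together. Maintenance patients have their own first and second cycle if the restarted calendar in Section 8.12 governs, and the opening rule then applies to them. The closing sentence sends the same patients to a table that can require a hold and a reduction. Because that table and its section are captioned as excluding hematologic toxicity, a site that follows the cross-reference finds a caption saying the table does not apply.

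Two sites could therefore act differently on the same count, and both could defend it from the text. Any hold uses up time under Section 8.7.4, which caps a cycle delay at 28 days and discontinues a patient once drug has been held for 56 days or more in total. The choice of reading can thus reach dose level and withdrawal from the study, and maintenance exposure and tolerability would partly reflect how each site read the section.

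**Working it through.** The plan gives no statistical figure to reproduce here, so the check is a comparison of text followed by one worked case.

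**Possible readings of Section 8.7.2 for a maintenance patient**

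- Reading A: the two-cycle rule applies in maintenance. Support: the heading covers both phases, the rule is not limited to reinduction, the calendar restarts at cycle 1, and the sentence opening the post-cycle-2 guidelines stands before everything after it, including the closing sentence. Table 8.5 would then govern counts only from maintenance cycle 3.
- Reading B: the closing sentence replaces the two-cycle rule. Support: it is specific to post-transplant patients, and the reason given for the rule concerns counts at presentation with leukemia. Table 8.5 would then govern counts from the start of maintenance.
- Reading C: the first two cycles means the patient's first two cycles overall. For anyone who completed two reinduction cycles, this gives the same order as B.

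No sentence in Sections 8.3, 8.7 or 8.12 chooses among these.

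**Worked case (an illustrative patient, not one from the documents)**

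Inputs, counts in x10^9/L:

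- Appendix VI: grade 3 neutrophils are below 1.0 down to 0.5, and grade 4 below 0.5. Grade 3 platelets are below 50 down to 25, and grade 4 below 25. Grade 1 extends down to 1.5 for neutrophils and 75 for platelets.
- Section 9.1: CRi has neutrophils below 1.0 or platelets below 100.
- The patient restarts after transplant with neutrophils 1.2 and platelets 60. Since 60 < 100, this is compatible with CRi.
- On maintenance cycle 2 day 1, neutrophils are 0.8 and platelets 40. Since 0.5 ≤ 0.8 < 1.0 and 25 ≤ 40 < 50, both are grade 3.

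Timing: two cycles are 2 x 28 = 56 days. Cycle 2 day 1 is day 29, inside that window. It is also the start of a planned cycle, the time at which the Table 8.5 caption says to take the grade. The next cycle start, day 57, is outside the window. Cycle 2 day 1 is therefore the clearest point at which the two rules meet.

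| Reading | Order on maintenance cycle 2 day 1 |
|---|---|
| A | Continue at the same dose |
| B (and usually C) | Hold; after recovery restart one level lower, for example 200 to 180 mg/m²/day on Table 8.6 |

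The end of the hold is also unclear. If baseline means the counts at maintenance restart, the patient recovers at 1.2 and 60. If that baseline is not meant, the grade 1 limits of 1.5 and 75 apply. The documents do not say which baseline Table 8.5 uses, and the answer changes how many days count toward the 28-day and 56-day limits.

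**Reach**

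Section 9.1 defines responders as relapsed or refractory patients treated as reinduction, so the response rate does not depend on how maintenance doses are modified. The patients concerned are those of the 14 planned who reach transplant and resume drug; the documents do not give that number.

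**The case against.** The strongest reply is that a specific sentence displaces a general one. The closing sentence names post-transplant patients, the reason behind the two-cycle rule describes active leukemia, and Section 7.1 restricts maintenance to patients in remission. The opening rule says only that no changes are planned, which is weaker than a prohibition. The calendar restart stands under follow-up visits and does not say that dose-modification rules restart with it. All of this stands as a reasonable reading, and on it there is no contradiction, only an unstated order of precedence and a mismatched caption. It does not settle the matter, because nothing in the section marks the closing sentence as an exception.

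Several stronger claims are tempting, and the documents do not support them:

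- A reader might infer a flat contradiction. The exception reading above prevents that.
- A reader might infer that the count triggering action differs two-fold between phases, 0.5 and 25 in the Section 8.7.2 guidelines against 1.0 and 50 for grade 3. The 0.5 and 25 limits belong to one guideline, which also requires more than four consecutive weeks. Another suggests considering a hold at pre-cycle neutrophils below 1 and platelets below 100 with no residual leukemia.
- A reader might infer that every maintenance patient with a grade 3 or 4 count in the first 56 days is affected. The Table 8.5 caption uses the grade at the next cycle start, so a mid-cycle low that has recovered by then would not trigger a reduction under that instruction.
- A reader might infer that Table 8.5 cannot work for counts. It runs on CTCAE grades, Appendix VI grades neutrophils and platelets, and its recovery target includes return to baseline. Whether it is the right clinical rule is not a question for this review.

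**Conclusion.** The point holds as an unreconciled overlap. Section 8.7.2 does not say whether the two-cycle rule applies to post-transplant maintenance, and it sends hematologic toxicity to a section and table captioned for non-hematologic toxicity. Defensible readings give different orders for a patient with grade 3 or 4 counts at maintenance cycle 2 day 1: continue unchanged, or hold and restart one level lower. For clinically significant or persistent grade 2, the difference is between continuing and a hold followed by the same dose.

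The consequence is limited to maintenance exposure, tolerability and possibly discontinuation under Section 8.7.4. The primary response endpoint is not affected. The number of patients involved cannot be stated from the documents, and the worked counts are illustrative. The overlap in the first two maintenance cycles rests on taking the calendar restart in Section 8.12 as defining those cycles. The mismatch between the cross-reference and the captions does not depend on that assumption.

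**What to change.** The sponsor should reconcile the passages in the next amendment:

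1. State in Section 8.7.2 whether the two-cycle rule applies to post-transplant maintenance, and if so whether its cycles are counted from the restart.
2. Name the single hematologic rule that governs maintenance.
3. Make the cross-reference and the captions agree, either by changing the pointer in Section 8.7.2 or by changing the title of Section 8.7.1 and the caption of Table 8.5.
4. State what baseline means in Table 8.5 for a patient who restarts in CRi.

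Which rule is clinically right is for the sponsor to decide; no view is taken here. The cost is a few sentences and a caption, with no added procedures, visits or patients.
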